# 5.6.5 Additional Reporting Requirements for IND Holders

For Investigator-Sponsored IND Studies, some additional reporting requirements for the FDA apply in accordance with the guidance set forth in 21 CFR § 600.80.

Events meeting the following criteria need to be submitted to the Food and Drug Administration (FDA) as expedited IND Safety Reports according to the following guidance and timelines:

# 7 Calendar Day Telephone or Fax Report:

The Investigator is required to notify the FDA of any fatal or life-threatening adverse event that is unexpected and assessed by the investigator to be possibly related to the use of ranibizumab. An unexpected adverse event is one that is not already described in the ranibizumab Investigator Brochure. Such reports are to be telephoned or faxed to the FDA and Genentech within 7 calendar days of first learning of the event.

#### 15 Calendar Day Written Report

The Investigator is also required to notify the FDA and all participating investigators, in a written IND Safety Report, of any serious, unexpected AE that is considered reasonably or possibly related to the use of ranibizumab. An unexpected adverse event is one that is not already described in the ranibizumab investigator brochure.

Written IND Safety reports should include an Analysis of Similar Events in accordance with regulation 21 CFR § 312.32. All safety reports previously filed by the investigator with the IND concerning similar events should be analyzed and the significance of the new report in light of the previous, similar reports commented on.

Written IND safety reports with Analysis of Similar Events are to be submitted to the FDA, Genentech, and all participating investigators within 15 calendar days of first learning of the event. The FDA prefers these reports on a Medwatch 3500 form, but alternative formats are acceptable (e.g., summary letter).

# **IND Annual Reports**

# Copies to Genentech:

All IND annual reports submitted to the FDA by the Sponsor-Investigator should be copied to Genentech. Copies of such reports should be faxed to Genentech Drug Safety:

[contact] or [contact]

Study Close-Out

Any study report submitted to the FDA by the Sponsor-Investigator should be copied to Genentech. This includes all IND annual reports and the Clinical Study Report (final study report). Additionally, any literature articles that are a result of the study should be sent to Genentech. Copies of such reports should be mailed to the assigned contact for the study:

# 6.0 INVESTIGATOR REQUIREMENTS

#### 6.1 STUDY INITIATION

Before the start of this study, the following documents must be on file with Cole Eye Institute/Cleveland Clinic or its appointed representative:

- FDA correspondence letter assigning an IND number or an IND waiver letter
- Original U.S. FDA Form 1571 (if applicable)
- Original U.S. FDA Form 1572 (for all studies conducted under U.S. Investigational New Drug [IND] regulations), signed by the Principal Investigator (if applicable)
- The names of any sub-investigators must appear on this form.
   Investigators must also complete all regulatory documentation as required by local and national regulations.
- Current curricula vitae of the Principal Investigator
- Medical License
- Written documentation of IRB approval of the protocol (identified by Cole Eye Institute/Cleveland Clinic, protocol number or title and date of approval)
- IRB Approved protocol
- Fully executed contract
- Documentation of registration into clinical research website (e.g., www.clinicaltrials.gov) (as applicable)
- Investigator Brochure Signature Receipt

#### 6.2 STUDY COMPLETION

The following data and materials are required by Cole Eye Institute/Cleveland Clinic before a study can be considered complete or terminated:

• Laboratory findings, clinical data, and all special test results from screening through the end of the study follow-up period (if applicable)

- Case Report Forms properly completed by appropriate study personnel and signed and dated by the investigator (if applicable)
- Copies of protocol amendments and IRB approval/notification (if applicable)
- A summary of the study prepared by the Principal Investigator (will accept IRB summary close letter) (if applicable)
- All regulatory documents (e.g., curricula vitae for each Principal Investigator, U.S. FDA Form 1571 and 1572)

#### 6.3 INFORMED CONSENT

Informed consent documents will be provided to each subject.

The informed consent document must be signed and dated by the subject or the subject's legally authorized representative before his or her participation in the study. The case history for each subject shall document that informed consent was obtained prior to participation in the study. A copy of the informed consent document must be provided to the subject or the subject's legally authorized representative. If applicable, it will be provided in a certified translation of the local language.

Signed consent forms must remain in each subject's study file and must be available for verification at any time.

The following basic elements must be included:

- A statement that the study involves research, an explanation of the purposes of the research and the expected duration of the patient's participation, a description of the procedures to be followed, and identification of any procedures or drug used for purposes which are experimental
- A description of any reasonably foreseeable risks or discomforts to the patients
- A description of any benefits to the patient or to others which may reasonably be expected from the research. A description that there may be no benefit from this research.

- A disclosure of appropriate alternative procedures or courses of treatment, if any, that might be advantageous to the patient
- A statement describing the extent, if any, to which confidentiality records identifying the patient will be maintained and that notes the possibility that the FDA and the Cole Eye Institute/Cleveland Clinic and the drug manufacturer may inspect the records
- For research involving more than minimal risk, an explanation as to whether any compensation and any medical treatments are available should injury occur and, if so, what they consist of or where further information may be obtained
- An explanation of whom to contact for answers to pertinent questions about the research and research patient's rights, and whom to contact in the event of a research-related injury to the patient
- A statement that participation is voluntary, that refusal to participate will involve no penalty or loss of benefits to which the patient is otherwise entitled, and that the patient may discontinue participation at any time without penalty or loss of benefits to which the patient is otherwise entitled

# 6.4 INSTITUTIONAL REVIEW BOARD OR ETHICS COMMITTEE APPROVAL

This protocol, the informed consent document, and relevant supporting information must be submitted to the IRB/EC for review and must be approved before the study is initiated. The study will be conducted in accordance with U.S. FDA, applicable national and local health authorities, and IRB/EC requirements.

The Principal Investigator is responsible for keeping the IRB/EC apprised of the progress of the study and of any changes made to the protocol as deemed appropriate, but in any case the IRB/EC must be updated at least once a year. The Principal Investigator must also keep the IRB/EC informed of any significant adverse events.

Investigators are required to promptly notify their respective IRB/EC of all adverse drug reactions that are both serious and unexpected. This generally

refers to serious adverse events that are not already identified in the Investigator Brochure and that are considered possibly or probably related to the study drug by the investigator. Some IRBs or ECs may have other specific adverse event requirements that investigators are expected to adhere to. Investigators must immediately forward to their IRB/EC any written safety report or update provided by Cole Eye Institute/Cleveland CLinic (e.g., IND safety report, Investigator Brochure, safety amendments and updates, etc.).

#### 6.5 CASE REPORT FORMS

All CRFs should be filled out completely by appropriate personnel. The CRF should be reviewed, signed, and dated by the investigator.

All CRFs should be completed in a neat, legible manner to ensure accurate interpretation of data. Black ink is required to ensure clarity of reproduced CRF copies. When making changes or corrections, cross out the original entry with a single line, and initial and date the change. DO NOT ERASE, OVERWRITE, OR USE CORRECTION FLUID ON THE ORIGINAL.

#### 6.6 STUDY DRUG ACCOUNTABILITY

The Investigator is responsible for the control and distribution of study drug.

All partially used or empty containers should be disposed of at the study site according to institutional standard operating procedure.

#### 6.7 DISCLOSURE OF DATA

Subject medical information obtained by this study is confidential, and disclosure to third parties other than those noted below is prohibited.

Upon the subject's permission, medical information may be given to his or her personal physician or other appropriate medical personnel responsible for his or her welfare.

Data generated by this study must be available for inspection upon request by representatives of the U.S. FDA, national and local health authorities, the drug manufacturer and the IRB/EC for each study site, if appropriate.

# 6.8 RETENTION OF RECORDS

U.S. FDA regulations (21 CFR §312.62[c]) require that records and documents pertaining to the conduct of this study and the distribution of investigational drug, including CRFs, consent forms, laboratory test results, and medication inventory records, must be retained by the Principal Investigator for 2 years after the investigation is discontinued and the U.S. FDA and the applicable national and local health authorities are notified.

# 6.9 STUDY CLOSE-OUT

÷

Any study report submitted to the FDA by the Sponsor-Investigator should be copied to Genentech. This includes all IND annual reports and the Clinical Study Report (final study report). Additionally, any literature articles that are a result of the study should be sent to Genentech. Copies of such reports should be faxed to the assigned Clinical Operations contact for the study:

Lucentis IST Program [contact]

# **APPENDIX A**

#### **Study Flowchart**

Group 1: Monthly Treatment Group

		Asse	Assessments During Treatment (Months)-visit 30 days (+/- 7 days) after												
	Pretreatment		1				ast tre	atmen	t		1			Follow-Up Assessments	
	Screen*	0*	1	2	3	4	5	6	7	8	9	10	11	End of Study Month 12	Unscheduled Visit
Informed consent	х	х													
Demographic data	Х	х													
Medical history	Х	х													
Vital signs (pulse/BP)	Х	х	х	х	х	х	х	х	х	х	х	х	х	х	Х
Weight	Х													х	
Concomitant Medication	Х	х	х	х	х	х	х	х	х	х	х	х	х	х	Х
Slit Lamp Exam	Х	х	х	х	х	х	х	х	х	х	х	х	х	х	х
Fundus Examination	Х	х	х	х	х	х	х	х	х	х	х	х	х	х	х
ETDRS Manifest Refraction/Complete eye exam	Х	х	х	х	х	х	х	х	х	х	х	х	х	X	х
SDOCT both eyes	Х	х	х	х	х	х	х	х	х	х	х	х	х	х	х
Intravitreal Ranibizumab Injection		х	х	x	x	x	x	х	x	x	х	x	x		X**
AE monitoring	Х	х	х	х	х	х	х	х	х	х	х	х	х	х	х
Fluorescein Angiography	х				х			х						x	

\* Screening and visit at month zero may occur on the same day. \*\* If treatment criteria met as outlined and at least 4 weeks has passed since the last injection.

	Pretreatment	Asse visit	essme 30 da y	nts Dı ys (+/-	uring Treatment (Months) — 7 days) after last treatment	Follow-Up Assessments			
	Screen*	0*	1	2	Month 3-11, timing per T & E protocol	End of Study Month 12	Unscheduled Follow-up Visit		
Informed consent	х	х							
Demographic data	х	х							
Medical history	х	х							
Vital signs (pulse/BP)	х	х	х	х	Х	х	Х		
Weight	х					Х			
Concomitant Medication	Х	х	х	х	Х	Х	Х		
Slit Lamp Exam	х	х	х	х	Х	Х	х		
Fundus Examination	х	х	х	х	Х	Х	Х		
ETDRS Manifest Refraction/Comple te eye exam	Х	х	х	х	Х	Х	x		
SDOCT both eyes	х	х	х	х	х	Х	х		
Intravitreal Ranibizumab Injection		х	х	х	X		X***		
AE monitoring	Х	х	х	х	х	Х	Х		
Fluorescein Angiography	х				[X]**	х			

### Group 2: Treat and Extend Group

\* Screening and visit at month zero may occur on the same day. \*\* Angiography to be performed at month 3 visit and at the first visit after week 22 (~ 6 month visit). \*\*\* If treatment criteria met as outlined for group 2 and at least 4 weeks have passed since last injection. T & E: Treat and Extend

# APPENDIX B Pre-Injection Procedures for All Subjects

In order to minimize the risk of potential adverse events associated with serial intravitreal injections (e.g., endophthalmitis), aseptic technique will be observed by clinic staff involved in the injection tray assembly, anesthetic preparation, and study drug preparation and administration. Intravitreal injection procedures will be performed in accordance with standard injection procedures at the Cleveland Clinic.

The intravitreal injection procedure will be carried out under controlled aseptic conditions, which include the use of sterile gloves, and a sterile eyelid speculum (or equivalent). Adequate anesthesia and a broad-spectrum microbicide (e.g., betadine) should be given prior to the injection.

#### **APPENDIX C**

#### Analysis of Similar Events Template for IND Safety Reports

#### **IND Safety Report**

#### **Case Summary**

This section will be initiated by a research coordinator and may be modified by principal investigators if necessary. The case summary should describe the reported AE in detail, including a description of what happened and a summary of all relevant clinical information (e.g. medical status prior to the event, signs, symptoms, diagnoses, clinical course, treatment, outcome, etc.) The IND safety report should not identify the subject ID #, reporting investigator, or the site as this information may compromise the study blind.

#### **PREVIOUS REPORTS**

The information for this section comes from Principal Investigator and the search of similar events. This section should be written by the responsible principal investigator.

\* Select one of the following two statements after reviewing the search of similar events results.

Under IND \_\_\_\_\_(insert IND#), the following IND safety reports of similar AEs have been previously submitted:

MCN	Reported Event	Submission Date

Or

Under IND \_\_\_\_\_ (insert IND#), no IND safety reports of similar AEs have been submitted previously.

In addition to previously submitted IND safety reports of similar events, this section can also summarize pervious serious reports of the same/similar event that were considered unrelated to the investigational product at the time of the reporting. These events would remain blinded, unless a decision to unblind is made by an Independent Monitoring Committee for reasons of subject protection. The decision on what similar events to summarize in this section should be made after reviewing the similar events report generated by Clinical Data Management. If a safety signal is particularly worrisome (e.g., a study stopping type of event), a more extensive evaluation may be required.

#### Assessment of Relationship

After evaluation the new case report and reviewing any relevant previous reports of similar events, the PI selects one of the following boilerplate conclusion statements, if applicable. The PI may also craft an alternative conclusion.

Based on review of available data, **Cleveland Clinic** believes there is a reasonable possibility of a cause-and-effect relationship between administration of \_\_\_\_\_\_(insert study drug name) and the occurrence of \_\_\_\_\_\_(insert AE).

Additional information on risk factors and/or treatment of the AE may be provided if warranted.

Or

Based on review of available data, the **Cleveland Clinic** does not believe that there is a reasonable possibility of a cause-and-effect relationship between administration of \_\_\_\_\_(insert study drug name) and the occurrence of \_\_\_\_\_\_(insert AE).

Explain if warranted. Do not speculate.

Or

Based on review of available data, the **Cleveland Clinic** cannot establish or exclude the possibility of a cause-and-effect relationship between administration of \_\_\_\_\_(insert study drug name) and the occurrence of \_\_\_\_\_(insert AE).

#### Explain if warranted. Do not speculate.

After review of the clinical details and investigator's comments pertaining to this AE, and based on experience to date, the **Cleveland Clinic** does not believe that changes to the conduct of this clinical trial are warranted. *This statement can be modified if changes to the conduct of the clinical trial are made*.

# Appendix D: Quantitative Assessment of Ultra-widefield Angiographic Features in Diabetic Macular Edema Addendum

Examples of quantitative segmentation of leakage and ischemia in ultra-widefield angiography. Quality permitting, UWFA obtained during study will be assessed for quantitative changes.

Figure 1: Diabetic macular edema and proliferative diabetic retinopathy with automated identification of retinal vascular leakage (green). Longitudinal assessment following anti-VEGF treatment. Areas of segmentation (e.g., green) able to be quantified in absolute or relative fashions for area.

Figure 2: Diabetic macular edema and proliferative diabetic retinopathy with automated identification of neovascular leakage (yellow), ischemia (blue) and retinal vascular leakage (green). Longitudinal assessment following anti-VEGF treatment. Areas of segmentation (e.g., green, yellow, blue) able to be quantified in absolute or relative fashions for area.

#### Appendix E: Pre-Ranibizumab Assessment of Anti-VEGF Therapeutic Response.

 As part of the screening process for REACT, the medical records are reviewed for prior treatment, medical history, and ophthalmic history information for assessment of inclusion and exclusion criteria. The same medical record will be reviewed for specific data on functional (visual acuity) and anatomic (OCT) data on response to bevacizumab prior to exposure to ranibizumab in the trial. This will be performed in a retrospective fashion without any additional contact with study subjects or study interventions. Overall response to therapy as well as stratification to ranibizumab response will be assessed (e.g., dramatic responder vs nonresponder). Subjects would also be evaluated in the context of their bevacizumab response (nonresponder vs incomplete responder vs tachyphylaxis).

•

REACT Study

Safety and Efficacy of Intravitreal Ranibizumab for Diabetic Macular Edema Previously Treated with Intravitreal Bevacizumab: A Randomized Dual-Arm Comparative Dosing Trial (Phase:1/2):

IND 120427

NCT01982435

Statistical Analysis Plan

11-07-2013

Measures for this study will be summarized using means, range and standard error of the means (SEM).

Two-sided paired t-tests and two-sided unpaired t-tests will respectively be conducted to analyze efficacy endpoints between study initiation to end, and between monthly and Treat and extend injection regimens. Patients who exit the study early can be accounted for by using a last observation carried forward approach. Chi-squared analysis will be used to assess significant differences in ophthalmic adverse event frequency. All analyses will be performed using GraphPad Prism 5 (GraphPad Software, La Jolla, California, USA) with a significance level of 0.05 being assumed for all tests

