# 4.1.2 Inclusion Criteria

Subjects will be eligible if the following criteria are met:

- Ability to provide written informed consent and comply with study assessments for the full duration of the study
- Age > 18 years
- ETDRS best-corrected visual acuity of 20/25 to 20/320 in the study eye
- Willing, committed, and able to return for ALL clinic visits and complete all study related procedures
- At least 6 previous bevacizumab injections for diabetic macular edema in the last 12 months.
- At least 2 bevacizumab injections within 10 weeks and the most recent bevacizumab injection within 6 weeks of baseline study visits
- Persistent foveal-involving diabetic macular edema based on presence of intraretinal and/or subretinal fluid by SDOCT in the foveal center at study entry

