#### b. Administration

Group 1 will undergo monthly intravitreal injections of 0.3 mg ranibizumab administered 30 days (+/- 7 days) following the last treatment for 12 months. Injections will be performed with sterile technique as outlined in appendix B.

Group 2 will be assigned to a "treat-and-extend" protocol. Eyes will be treated with 3 loading doses at 30-day (+/- 7 days) intervals. After the third loading dose, the follow-up interval is determined with an OCT-based protocol:

• **Criterion A:** If the central subfield thickness is less than or equal to 300 microns or there is complete absence of intraretinal or

subretinal fluid on the macular cube, the follow-up interval is increased by 2 weeks (+/- 7 days) at each visit [to a maximum interval of 12 weeks (+/- 7 days)]. The eye receives an intravitreal ranibizumab injection at every visit.

- Criterion B: If on subsequent follow-up visits, the thickness increases above 300 microns or there is recurrence of fluid with thickness above 300 microns, the interval is reduced by 2 weeks (+/-7 days) (to a minimum interval of 4 weeks). Designated visits will also occur at 6 months and 12 months for visual acuity, ocular examination, FA, and OCT. No treatment will occur at these visits unless the time coincides with the scheduled "treat-and-extend" visit.
- Criterion C: Rescue criteria If on subsequent follow-up visits, a
  patient loses > 15 letters with associated recurrence of fluid or
  central subfield thickness above 300 microns, the dosing interval will
  be immediately reduced to 4 weeks (+/- 7 days) for the next followup visit and for the residual duration of the study.

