#### a. Primary Endpoint

- Incidence and severity of ocular adverse events, as identified by eye examination (including visual acuity testing)
- Incidence and severity of other non-ocular adverse events, as identified by physical examination, subject reporting, and changes in vital signs

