#### 4.8.3 Efficacy Analyses

#### a. Secondary Endpoints

- Mean change from baseline in best-corrected visual acuity by the number of letters read correctly at months 6 and 12.
- Mean absolute change from baseline central foveal thickness at months 6 and 12 as measured by SDOCT (defined as the average thickness within the central 1 mm subfield)
- Proportion of eyes that were anatomically "dry" by SDOCT at months 6 and 12.
- Proportion of eyes gaining greater than or equal to 15 letters of vision at months 6 and 12.
- Proportion of eyes losing greater than or equal to 15 letters of vision at months 6 and 12.
- Proportion eyes with 20/40 or better best-corrected visual acuity at months 6 and 12.
- Comparison of angiography leakage from baseline to months 3, 6, and 12.
- Comparison of peripheral nonperfusion from baseline to months 3, 6, and 12.
- Comparison of previous anatomic anti-VEGF response to month 3, month 6, and month 12 anatomic response.
- Comparison of previous functional anti-VEGF response to month 3, month 6 and month 12 functional response

٠

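### The SAP's only efficacy tests are t-tests, which suit no endpoint that is already a change from baseline: gain or loss of 15 letters would be tested against an all-zero baseline

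*SAP*

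**What the plan says.** The SAP is a single short section. On efficacy it states: "Two-sided paired t-tests and two-sided unpaired t-tests will respectively be conducted to analyze efficacy endpoints between study initiation to end". The same sentence gives the unpaired test to the comparison of monthly with treat-and-extend dosing. It does not restrict the tests to continuous endpoints. The only categorical method in the SAP is chi-squared, and it is confined to the frequency of ophthalmic adverse events. All tests use a 0.05 level. The only rule for summaries begins "Measures for this study will be summarized using means, range and standard error of the means (SEM"; counts, proportions and confidence intervals are not mentioned.

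Protocol section 4.8.3 (Efficacy Analyses) includes four proportions, each at two time points, and gives no test for any of them:

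- anatomy: the share of eyes that SDOCT shows to be *dry*;
- improvement in acuity: "Proportion of eyes gaining greater than or equal to 15 letters of vision at months 6 and 12";
- its mirror image, a loss of the same size or more;
- level of acuity, not change: "Proportion eyes with 20/40 or better best-corrected visual acuity at months 6 and 12".

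Two other places bear on the baseline value of *dry*. Inclusion criterion (section 4.1.2): "Persistent foveal-involving diabetic macular edema based on presence of intraretinal and/or subretinal fluid by SDOCT in the foveal center at study entry". Criterion A for extending the interval (section 4.3.2b) can be met either by a thin enough retina or by absence of fluid; it opens "If the central subfield thickness is less than or equal to 300 microns or there is complete absence of intraretinal or". *Dry* itself is not defined.

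The primary endpoint (section 4.8.2a) has an ocular part and a non-ocular part; the second reads "Incidence and severity of other non-ocular adverse events, as identified by physical examination, subject reporting, and changes in vital signs". Section 3.4 says that the study is not powered for severe events and cannot settle the incidence of rare ones.

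**The concern.** A paired test needs a value at the start and a value at the end. Gain and loss of 15 letters have no separate starting value, because each compares the later visit with baseline. Entered into the planned paired test, the starting column is zero for every eye. The null hypothesis is then that no eye ever changes by 15 letters, which is of no clinical interest. A few eyes moving in either direction will reject it, and gain and loss can both be significant in the same data. A p-value below 0.05 for gain could be read as evidence of improved vision when mean acuity is unchanged or worse.

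The summary rule raises a similar problem for the primary endpoint. If no patient has a given event, the mean is 0 and the SEM is 0, so the table shows no uncertainty for exactly those rare events where uncertainty is large.

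**Working it through.** **Inputs.** 30 patients, 15 per arm (protocol section 3.1); two-sided tests at 0.05 (SAP); severe ocular risk of about 1/1000 (protocol section 3.4). Sample size was chosen for feasibility (section 4.8.1), so there is no power figure to reproduce.

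**1. Paired t-test against an all-zero baseline.** Let k of n eyes score 1 at the end and all score 0 at the start. The mean difference is k/n and its SEM is √[k(n−k)/(n²(n−1))], so

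t = √[k(n−1)/(n−k)], on n−1 degrees of freedom.

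| n | k | t | two-sided p |
|---|---|---|---|
| 30 | 3 | √(3×29/27) = 1.795 | 0.083 |
| 30 | 4 | √(4×29/26) = 2.112 | 0.043 |
| 15 | 3 | √(3×14/12) = 1.871 | 0.082 |
| 15 | 4 | √(4×14/11) = 2.256 | 0.041 |

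The smallest k giving p<0.05 is 4 at every n from 5 to 30, so dropout does not move the threshold.

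**2. What the result can sit beside (invented data, 30 eyes).**

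- 4 eyes gain 15 letters, 4 lose 15, 22 are unchanged. Mean change is 0 (p=1.0). The gain test and the loss test each give p=0.043.
- 4 gain 15, 12 lose 15, 14 are unchanged. Mean change = (60−180)/30 = −4.0 letters; SD = √[(16×225 − 30×16)/29] = 10.37; t = −4.0/(10.37/√30) = −2.11; p=0.043, a worsening. The gain test still gives p=0.043. The loss test gives t = √(12×29/18) = 4.40, p=0.0001.

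**3. An informative summary of the same counts.** Clopper-Pearson 95% intervals: 4/30 = 13.3% (3.8% to 30.7%); 4/15 = 26.7% (7.8% to 55.1%).

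**4. The other two proportions.** *Dry*: entry requires foveal fluid, so baseline is zero for every eye if *dry* means fluid-free. Under wording like Criterion A, where thickness of 300 microns or less is enough, some eyes could qualify at entry. 20/40 or better: entry acuity runs from 20/25 to 20/320 (section 4.1.2), so baseline varies and a paired comparison has a real null. Enumerating all outcomes with improvement and worsening equally likely, and 10% to 50% of eyes changing status (an assumed range, in 5-point steps), the paired t-test rejects in at most 5.0% of samples at n=15 and 4.8% at n=30. It holds its level.

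**5. Zero adverse events.** SEM = 0. The exact two-sided 95% upper limit is 1 − 0.025^(1/n): 11.6% at n=30 and 21.8% at n=15. Section 3.4 does not say whether 1/1000 is per injection or per patient. Per patient, P(no severe ocular event) = 0.999^30 = 97%. Per injection, assuming at most 30×12 = 360 scheduled study-eye injections, it is 0.999^360 = 70%. Zero is the likeliest count either way. For a common event the choice matters little: at 10/30, mean ± t×SEM gives 15.4% to 51.2% and the exact interval 17.3% to 52.8%.

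**The case against.** The strongest reply is that the SAP sentence applies to quantities compared from initiation to end, which presupposes a measurement at both times. Acuity letters and thickness have one; gain and loss of 15 letters do not, and no document asks anyone to construct a column of zeros. This reading is reasonable, and on it the 4-eye result never arises. It does not remove the need for the edit: chi-squared is reserved for ophthalmic events, so the listed proportions would then have no stated method.

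A second reply is that nobody would be misled, because mean letter change and loss are reported alongside. In the second invented example a reader would also see a significant mean worsening and p=0.0001 for loss. That stands, and it limits the harm. The gain p-value still carries no information of its own.

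A third is that adverse events would be tabulated as counts anyway, since the endpoint is incidence and the SAP speaks of event frequency. That is likely, and section 3.4 already concedes that rare-event incidence cannot be determined. What remains is that the stated summary rule gives no interval.

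A reader might infer that all four proportions are wrongly analysed. The documents do not support that: the problem is shown for two, depends on a missing definition for *dry*, and is not shown for 20/40 or better. A reader might also infer that the between-arm t-test is invalid for proportions. Results can differ from an exact test (0/15 against 4/15: unpaired t p=0.032, Fisher p=0.100), but that comparison has a meaningful null and no error is claimed there.

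**Conclusion.** The point holds as a minor one. The SAP gives efficacy endpoints only t-tests, and everything only mean, range and SEM, although four listed efficacy endpoints are proportions. For gain and loss of 15 letters the initiation-to-end test, applied as written, crosses 0.05 at 4 eyes, whether pooled or per arm, and is not evidence of benefit. If the authors intended a narrower scope, the gap is an unstated method instead. The same problem reaches *dry* only if it means fluid-free.

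The safety part is narrower still: for event types with no cases, SEM 0 hides an upper limit of 11.6% overall or 21.8% per arm. It would be too strong to infer that the trial claims to settle rare-event rates, because section 3.4 says the opposite.

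The arithmetic in steps 1, 3 and the zero-event limits needs no outside figure. The examples in step 2 are invented, and the 70% rests on the assumed 360 injections. These are secondary endpoints and a matter of presentation in a 30-patient pilot; the primary outcome is safety and nothing here undermines the randomised comparison.

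**What to change.** In the SAP:

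- limit paired t-tests to continuous measures, such as acuity letters and central foveal thickness;
- report the four proportions, and the incidence of ocular and non-ocular adverse events, as n/N with exact (Clopper-Pearson) 95% intervals, per arm and overall;
- state that no initiation-to-end test is done for gain or loss of at least 15 letters;
- define *dry* for the analysis, and omit its initiation-to-end test too if it means fluid-free.

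Exact McNemar for 20/40 or better is optional, not the correction of an error. It is stricter: with 4 eyes improving and none worsening among 30, the paired t-test gives p=0.043 and exact McNemar gives 2×0.5⁴ = 0.125.

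The cost is two or three sentences and no new data. A few within-group secondary p-values disappear.
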